3. STUDY POPULATION

3.1 List the number of subjects to be enrolled

We will recruit 74 patients in total, and with a dropout rate of 15%, we will have a sample size of 64. With 64 patients, 32 in each group, we can detect a large effect size with 1 degree of freedom, alpha of 0.05 at 80% power.

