3.3 Inclusion Criteria

Sixty-four subjects will be recruited amongst patients attending the Clinic for Graduate Periodontics, Graduate Prosthodontics, or the UTDentists, who have at least one implant with peri-implant inflammation that requires non-surgical treatment. Peri-implant diseases included are peri-implant mucositis and peri-implantitis. All subjects will be ≥ 18 -year-old and systemically healthy or with controlled common systemic conditions, such as hypertension, that will not affect wound healing. Criteria for diagnosis of peri-implant mucositis or peri-implantitis:

1. Red, swollen gingival tissues surrounding the implant
2. Presence of bleeding and/or suppuration on gentle probing around the implant
3. Increased probing depth compared to probing depth after restoration of the implant (greater than 2mm increase in probing depth)
4. May or may not have progressive bone loss in relation to radiographic bone levels assessed either 1 year following restoration of the implant OR ≥ 3 mm of radiographic bone loss from the implant platform

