6. METHODS AND ASSESSMENTS

6.1 Randomization and Blinding

Therapy group allocation (test or control) will be performed by the investigators before treatment is rendered based on computer-generated randomized (R Statistical Software). Two blinded examiners will be used to take clinical measurements (presence/absence of Plaque, BOP, PPD, CAL) at baseline, and then six and twelve weeks after treatment. Patients in the control group will be blinded by performing mechanical debridement plus a “sham” aPDT (saline with non-light emitting laser).

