The twelve weeks follow up will be the subjects last visit for this clinical trial. The patient will have clinical measurements taken as previously mentioned as well as possible radiographic measurements. If the patient has been diagnosed with peri-implant mucositis, recommendations will be made for continued maintenance of the diseased implant(s) and follow every 3 months. If the patient has been diagnosed with peri-implantitis, recommendations will be made for the possible need for surgical treatment.

d. Post Study Follow up and Procedures

[figure not shown]
The subjects will continue having routine maintenance appointments and/or treatments to follow up the outcomes related to the surgery and periodontal health in the periodontics clinic of UTSD. If the patients have symptoms or complications, the necessary treatments, will be performed.

e. Discontinuation Visit and Procedures

Subjects are free to withdraw from participation in the study at any time upon request. A subject may be discontinued from participation in the study for any of the following reasons:

1. Withdrawal of consent
2. Subject noncompliance with the protocol, as determined by the investigator
3. Any event or condition that would make continued participation in the study not in the best interest of the subject, as determined by the investigator
4. Pregnancy
5. Development of any medical condition that might affect the treatment and clinical outcomes, as determined by the investigator.
6. Initiation of any treatment or exposure that might affect the outcomes of implant therapy, as determined by the investigator.
7. Investigator discretion

Any subject with a serious adverse event, such as life-threatening diseases, hospitalization, that is ongoing at the time of discontinuation will be followed until the event returns to baseline, resolves, or stabilizes. If the serious adverse event does not meet these outcomes within 30 days after discontinuation or after study completion, the subject will be referred to an appropriate practitioner for continued care. If the study is discontinued, subjects will be referred back to the qualified clinicians for necessary dental care.

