11. SAMPLE SIZE AND STATISTICAL METHODS

11.1 Determination of Sample Size

We will recruit 74 patients in total, and with a dropout rate of 15%, we will have a sample size of 64. With 64 patients, we can detect a large effect size with 1 degree of freedom at an alpha equal to 0.05 with 80% power between the two treatments.

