11.2 Statistical and Analytical Plans

a. General Consideration

We will present means and standard deviations for completeness of the report. The statistical significance level to test the primary endpoint was set at $p<0.05$.

b. Safety Analyses

Safety will be evaluated by tabulations of adverse events and will be presented with descriptive statistics at baseline and follow-up visits each month.

Adverse events will be classified as severe complications and summarized for baseline and follow-up visits.

All information pertaining to adverse events noted during the study will be listed by subject, detailing verbatim given by the investigator, preferred term, date of onset, date of resolution, severity, and relationship to procedure. The onset of adverse events will also be shown relative (in number of days) to the day of performing the surgery.

c. Statistical Analysis Plan

We will analyze these data sets using generalized linear mixed effects models with the appropriate error structure (e.g., binomial, poisson) and specifying treatment (control mechanical debridement vs mechanical debridement + aPDT) as a fixed factor and repeated measures of individuals over 0, 6, and 12 weeks as a random factor. Demographic data collected from patients will be included in analysis and will be adjusted for any confounders. All quantitative analyses will be performed in R Statistical Software (R Core Team 2017).

For microbiologic analysis, microbial DNA will be purified using the QIAmp DNA Mini Kit (Qiagen, Hilden, Germany) or Qiagen DNA MiniAmp kit (Qiagen, Valencia, CA, USA), according to the manufacturer's protocol. 16S rRNA gene V4 amplification and sequencing will be completed. 16S rRNA gene data analysis will also be completed for the plaque samples.

For immunologic analysis, the PerioPaper strips will be analyzed using multiplexed fluorescent bead-based immunoassay. Assessments will be made in triplicate, and for the statistical analysis, median of the replicates will be used.

12. Ethical Consideration

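### Mucositis and peri-implantitis are pooled, but baseline diagnosis is neither a described randomisation stratum nor a prespecified model term, and the covariate adjustment has no fixed list

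*Combined protocol and SAP*

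**What the plan says.** **Population.** Section 3.3 states: "Peri-implant diseases included are peri-implant mucositis and peri-implantitis". Section 5.1 confirms one diseased implant per patient and a single comparison across both diagnoses. No quota or expected mix is given.

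**Allocation.** Section 6.1 has the investigators allocate "before treatment is rendered based on computer-generated randomized (R Statistical Software"). It mentions no strata, blocks or minimisation.

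**Model.** Section 11.2c specifies a generalised linear mixed model with treatment as the fixed factor and repeated measures on individuals at weeks 0, 6 and 12 as the random factor. It then adds: "Demographic data collected from patients will be included in analysis and will be adjusted for any confounders". Diagnosis is not named as a covariate, interaction or subgroup.

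**Other text that bears on this.** Section 2.2 plans a multivariate analysis relating demographic and implant variables to the two diagnoses, which is not an adjustment of the treatment comparison. Section 6.3a lists dental conditions and implant data under its demographic heading, and collects radiographic information before treatment.

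**Signs that the diagnoses differ in course.** Section 1.1 calls mucositis reversible by plaque removal and ties peri-implantitis to bone loss and increasing probing depth. In section 6.3c, mucositis leads to maintenance advice, whereas for the other diagnosis: "If the patient has been diagnosed with peri-implantitis, recommendations will be made for the possible need for surgical treatment".

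**The concern.** A baseline factor that the protocol itself treats as separating two clinical courses should be fixed in the primary model of a trial with 32 evaluable patients per arm. The plan does not do this, while it leaves the covariate set open. Two things follow.

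- A chance excess of peri-implantitis in one arm can move the treatment estimate in this one trial. Any outcome variance that diagnosis explains stays in the error term if diagnosis is left out.
- Because the adjustment set has no list and no rule, several models are all consistent with the plan. A reader of the result could not tell which one had been intended.

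**Working it through.** **1. The plan's own figure.** Section 3.1: "With 64 patients, 32 in each group, we can detect a large effect size". Section 11.1 puts this at alpha 0.05 and 80% power with 1 degree of freedom. The large effect is never given a number, so 64 cannot be reproduced. Assuming a two-sided t-test:
- 32 per arm has 80% power for d = 0.71. The normal approximation gives (1.960 + 0.842) × √(2/32) = 0.70.
- At the conventional d = 0.8, 26 per arm would be enough.

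The sample size is not in dispute here; d = 0.71 is only the reference for step 4.

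**2. Chance imbalance in diagnosis.** The inputs are 74 patients recruited (section 11.1), simple 1:1 randomisation (assumed, since section 6.1 describes no restriction) and a peri-implantitis share p of 30% to 50% (assumed). With 37 per arm, the SD of the between-arm difference in share is √(2p(1−p)/37), which is 0.107 at p = 0.30 and 0.116 at p = 0.50. Results by simulation of simple randomisation at 74, and by exact binomial calculation at 32 per arm:

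| Patients | p | gap ≥ 15 points | gap ≥ 20 points |
|---|---|---|---|
| 74 recruited | 0.30 | 16% | 6% |
| 74 recruited | 0.50 | 20% | 9% |
| 64 evaluable | 0.30 | 22% | 8% |
| 64 evaluable | 0.50 | 26% | 10% |

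At p = 0.20 with 64 evaluable, the figures are 16% and 4%.

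**3. What an imbalance does to an unadjusted difference.** Shift = gap in share × difference in outcome between diagnoses, in SD units. The documents give no value for the second factor. For a 20-point gap:
- 0.25 SD assumed: 0.20 × 0.25 = 0.05 SD, or 7% of the detectable 0.71.
- 0.5 SD assumed: 0.20 × 0.5 = 0.10 SD, or 14%.
- 1.0 SD assumed: 0.20 × 1.0 = 0.20 SD, or 28%.

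These shifts apply to an unadjusted between-arm comparison, which is not the planned analysis.

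**4. Precision from including diagnosis.** If diagnosis explains a share R² of outcome variance (assumed), the residual variance is multiplied by 1 − R². The noncentrality becomes 0.711 × √(32/2) / √(1 − R²), with 61 degrees of freedom, and the unadjusted equivalent is 64 / (1 − R²).

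| R² | power | equivalent unadjusted N |
|---|---|---|
| 0 | 80% | 64 |
| 0.02 | 81% | 65 |
| 0.05 | 82% | 67 |
| 0.10 | 84% | 71 |
| 0.20 | 88% | 80 |

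These credit diagnosis alone. Once the baseline outcome is in the model, the added R² falls to the extent that diagnosis and baseline are correlated.

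**The case against.** **Diagnosis may already be covered.** Section 11.2c says demographic data will be included, and section 6.3a puts dental and implant data under that heading. This stands as far as it goes: a reader might infer that the plan excludes diagnosis, and the text does not say so. But wording that allows diagnosis without requiring it is not prespecification.

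**Data-driven selection is not stated.** A reader might infer that covariates will be chosen from observed imbalance. The plan gives no selection rule, so this is permitted but not announced. What can be shown is the missing list.

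**Prognostic strength is not established.** A reader might infer that diagnosis is the strongest predictor of 12-week change. The documents do not say this. Mechanical debridement is called the gold standard for peri-implant inflammation generally, and section 3.3 lists bleeding or suppuration and increased probing depth among the criteria for both diagnoses. At an R² of 0.02 to 0.05 the gain is small.

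**The repeated-measures model may absorb part of the imbalance.** Week 0 is among the responses, and section 2.2 frames the outcome as change. If the effect is read as change from baseline, a stable level difference between diagnoses is partly removed, though a difference in response to treatment would remain. Section 11.2c names no time or treatment-by-time term, however, so that reading is not secured.

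**Randomisation is unbiased.** This is correct. A reader might infer a biased design, but the issue is chance imbalance in one small trial, together with precision.

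**Conclusion.** The point holds in a limited form. The two diagnoses are pooled, no stratum is described, diagnosis is not a prespecified term, and the adjustment set is open. The comparison is unbiased on average, but a gap of at least 15 points arises by chance in about 16-20% of trials of 74, and at least 20 points in about 6-9%, assuming simple randomisation and a share of 30% to 50%.

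The benefit of naming diagnosis ranges from slight (power 81-82% at an R² of 0.02 to 0.05) to useful (84-88% at 0.10 to 0.20), and is less with baseline in the model. Neither the case mix nor R² is in the documents. The shift of 0.10-0.20 SD in step 3 should not be read as the expected error of the planned model. The change is worth making because it is nearly free and removes discretion from the primary analysis, not because the design is invalid.

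**What to change.** **Section 11.2c.** Replace the confounder sentence with a fixed primary model containing treatment, baseline diagnosis and the baseline value of the outcome.
- Define diagnosis usably: peri-implantitis if the radiographic bone loss described in section 3.3, criterion 4 is present, and mucositis if it is absent, recorded before allocation. Criterion 4 cannot serve as it stands, because it is met with or without bone loss.
- If baseline is a covariate, remove week 0 from the response vector. Alternatively, keep week 0 as a response and add time and treatment-by-time terms instead of the baseline covariate.
- Put all other covariates in sensitivity analyses only.

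**Section 6.1 (optional, only if enrolment has not begun).** Stratify the R list by diagnosis, with randomly varying block sizes concealed from the investigators who allocate and treat.

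**Cost.** A few lines of text and code. Diagnosis must be classified before allocation: section 6.3a collects radiographs before treatment, but does not say that the two diagnoses are separated before allocation. Stratified blocks make allocation slightly more predictable, which matters because investigators allocate and the treating investigator is unblinded. If enrolment has begun, the model change alone can still be made before any unblinded analysis.

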2.3 Secondary Outcome Measures

In addition to the clinical outcomes, plaque samples and peri-implant sulcular fluid (PISF) will be taken to assess the microbiologic and immunologic profile before and after treatment with or without aPDT. Subgingival biofilm samples will be collected using sterile titanium implant scalers and will be assessed at baseline and week 12 follow up. PISF will be collected from the tested implant site after clinical examination. The levels of interleukin (IL)-1 α , IL-1 β , IL-6, IL-8, IL-10, IL-12, IL-7A, tumor necrosis factor (TNF)- α , C-reactive protein, osteoprotegerin, leptin, and adiponectin will be determined using multiplex proteomic immunoassays.

2.4 Potential Risks and Benefits:

a. End Point – Efficacy

All eligible patients needing non-surgical treatment of peri-implant disease will receive the appropriate treatment of mechanical debridement. The mechanical removal of plaque around the implants is the gold standard of care in the treatment of implant inflammation. The patients in the adjunctive aPDT group may have improved healing as observed through surrogate clinical measures of inflammation (BOP, PPD), greater microbiologic reduction, and levels of key biomarkers in PISF that resembles peri-implant tissue health (Recker 2015).

b. End Points – Safety

1) Study related risks:

Initial mild pain, swelling, and bleeding related to non-surgical implant surface mechanical debridement. Potential for antimicrobial methylene blue dye to reversibly stain gingiva around implant site. Collecting PISF will not result in any additional side effects. Patient will not be provided medications for study

related pain. If patient reports pain after treatment will recommend over the counter analgesics such as ibuprofen or acetaminophen.

2) Protection against risk:

All efforts will be made to minimize risks to all and every participant. Laser safety protocols will be followed including laser safety mechanisms, labels and signage, safety zone implementation, proper eye protection for patient and clinician.

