6.3 Study Visits and Procedures

a. Screening Visits and Procedures

Study protocol and consent forms will be approved by the Institutional Review Board at the University of Texas Health Science Center at Houston. The trial will be registered with ClinicalTrials.gov. The clinicians treating patients at UTSD will be told the information of this clinical trial. The potential subjects will be identified in the clinic of Department of Periodontics, Prosthodontics, or UTDentists for initial screening. The principal investigator will confirm the eligibility of these patients.

All patients will sign the consent forms and will be informed of the details of study procedures as well as potential complications. After informed consent is obtained, the non-surgical implant therapy will be scheduled as the first visit.

Patient's Demographic Data Collection

Upon enrollment into the study and patient's consent form signed, patient's demographic data from patient's electronic health record (EHR) in the UT School of Dentistry will be collected. This information will include, but not limited to, patient's de-identifiable chart number, age, gender, race, medical history, dental conditions, and all pertinent dental implant related data. Radiographic information regarding the implant(s) included in the study will also be collected prior to treatment.

b. Study Visits and Procedures

Patients will be randomly divided into 2 treatment groups. (A) Test group: patients will undergo traditional non-surgical mechanical debridement with adjunctive use of aPDT at implant(s). (B) Control group: patients will undergo traditional non-surgical mechanical debridement alone with “sham” aPDT with saline and non-light emitting laser at implant(s). Clinical measurements and PISF will be collected at the baseline appointment, and at follow up 12 weeks after treatment. For PISF collection, the volume of fluid collected will be measured using Periotron then stored in -80° C freezer. Plaque samples will be taken at baseline and at the 12-week appointment. Full mouth prophylaxis or periodontal maintenance will be completed with ultrasonics, hand instruments, and prophylaxis paste. Oral hygiene instructions will be

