Plaque samples will be taken from the deepest probing site of each implant before and 12 weeks after PDT. If more than one sites presented similar probing values, the most anterior site would be chosen for ease of obtaining an appropriate sample. The sample sites will first be isolated by cotton rolls and supragingival and marginal plaque will be removed before subgingival biofilm samples collected using sterile titanium implant scalers (Hu-Friedy). The collected samples will be immediately placed in separate sterile Eppendorf tubes containing 0.15 ml TE (10 mM Tris-HCl, 1 mM EDTA, pH 7.6). Samples will be stored at -80°C until further analysis. DNA will be purified using the QIAamp DNA Mini Kit (Qiagen, Hilden, Germany) or Qiagen DNA MiniAmp kit (Qiagen, Valencia, CA, USA), according to the manufacturer's protocol. 16S rRNA gene V4 amplification and sequencing will be completed. 16S rRNA gene data analysis will also be completed for the plaque samples.

PISF collection and analysis

PISF will be collected from the sulcus around the target dental implant using paper strips (PerioPaper, Oraflow). In patients with multiple implants, preference will be given to the implant included in the study. With proper isolation using cotton rolls in the buccal and lingual aspects of the study site, the area will be dried for 5 seconds with compressed air. The paper strip will be gently introduced into the

mucosal crevice around the dental implant for 30 seconds per site in four sites (mesial, distal, facial/buccal, lingual/palatal). The strips will then be removed from the crevice, and the volume of fluid collected in each strip measured using a micromoisture metering device (Peritron, Oraflow). After confirming the adequateness of the volume, the paper strips from each implant will be transferred into labeled tubes and stored at -80° C for later use. For analysis, the paper strips will be analyzed using multiplexed fluorescent bead-based immunoassay. Assessments will be made in triplicate, and for the statistical analysis, median of the replicates will be used.

c. Final Study Visit

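### The SAP states no week-12 contrast for the 12 PISF biomarkers; read literally, its model roughly halves a week-12 difference, and neither the scale nor an error policy is fixed

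*Combined protocol and SAP*

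**What the plan says.** Section 2.3 lists 12 PISF biomarkers as a secondary outcome, to be compared before and after treatment, with and without aPDT. It calls them only levels, which "will be determined using multiplex proteomic immunoassays". Section 2.4a counts biomarker levels resembling healthy tissue among the possible benefits of aPDT.

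Section 6.3 gives the sampling: "Clinical measurements and PISF will be collected at the baseline appointment, and at follow up 12 weeks after treatment". Strips stay in the crevice for 30 seconds at each of four sites, with "the volume of fluid collected in each strip measured using a micromoisture metering device". The only stated use of that volume is a check that it is adequate before storage.

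Section 11.2c names the assay ("For immunologic analysis, the PerioPaper strips will be analyzed using multiplexed fluorescent bead-based immunoassay") and the median of triplicates. Its one model is a generalized linear mixed model with treatment as a fixed factor and "repeated measures of individuals over 0, 6, and 12 weeks as a random factor". Demographic variables may be adjusted for; the baseline value of the outcome is not mentioned. Section 11.2a sets the 0.05 level for the primary endpoint only. No section names a lead biomarker, a multiplicity method or an exploratory status.

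**The concern.** Three things needed to turn 12 assay readings into a treatment comparison are left open.

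- **Contrast.** The question is whether the arms differ at week 12, given where each implant started. A model with treatment as its only named fixed factor, fitted to visits that include baseline, does not estimate that. Its treatment coefficient is an average over visits, one of which precedes treatment.
- **Scale.** With timed collection, total amount and concentration are different variables whenever fluid volume differs. Volume may respond to a treatment meant to reduce inflammation.
- **Error policy.** Twelve comparisons with no rule leave a reader unable to say what one nominally significant biomarker means.

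At stake is the biomarker conclusion: a real week-12 effect could be understated, and the analyst would choose the scale and the number of reported tests after seeing data. The primary BOP and PPD results are not touched by this point.

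**Working it through.** **The plan's own figures.** Section 11.1: "We will recruit 74 patients in total, and with a dropout rate of 15%, we will have a sample size of 64". Check: 74 × 0.85 = 62.9 and 64 × 1.15 = 73.6, so 64 and 74 agree to within rounding or the direction of inflation. Section 3.1 gives 32 per arm. At that size, 80% power at two-sided 0.05 corresponds to a standardised difference of (1.96 + 0.84) × √(2/32) = 0.70, or 0.71 by the t distribution. The plan gives no power or error rate for biomarkers, so these figures supply only the 32 per arm used below.

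**1. What the literal model estimates.** Let δ be the true between-arm difference at week 12 on the analysed scale. Randomisation makes the expected baseline difference 0. With two visits, balanced data and a random subject effect, the treatment coefficient equals the between-arm difference in subject means:

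(0 + δ)/2 = δ/2.

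Precision does not make up for this. Assume equal variance σ² at both visits and within-patient correlation r (not given in the documents). A subject mean has variance σ²(1 + r)/2, and the week-12 value adjusted for baseline has variance σ²(1 − r²). The ratio of expected test statistics, literal model to ANCOVA, is

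(1/2) × √[(1 − r²) / ((1 + r)/2)] = √[(1 − r)/2].

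| r (assumed) | ratio |
|---|---|
| 0.3 | 0.59 |
| 0.5 | 0.50 |
| 0.7 | 0.39 |

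If PISF were also taken at week 6 with the same effect δ, the coefficient would be (0 + δ + δ)/3 = 0.67δ, still too small.

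**2. Scale.** Concentration = amount / volume, so the between-arm (aPDT/control) ratios satisfy: concentration ratio = amount ratio / volume ratio. All inputs here are assumed.

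| amount ratio | volume ratio | concentration ratio |
|---|---|---|
| 0.80 | 0.90 | 0.89 (same direction) |
| 0.80 | 0.80 | 1.00 (no difference) |
| 0.85 | 0.70 | 1.21 (opposite) |
| 0.80 | 0.60 | 1.33 (opposite) |

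When the amount ratio is below 1, the sign changes only if the volume ratio is lower still. A proportional fall in volume common to both arms cancels.

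**3. Error rate across 12 tests.** Assume each biomarker is tested two-sided at 0.05 and none truly differs. Under independence:

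- any false difference: 1 − 0.95^12 = 0.46; expected number 12 × 0.05 = 0.6
- any false difference in the favourable direction: 1 − 0.975^12 = 0.26

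For equally correlated biomarkers, by simulation:

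| correlation | any direction | favourable direction |
|---|---|---|
| 0 | 46% | 26% |
| 0.3 | 40% | 20% |
| 0.5 | 32% | 16% |
| 0.7 | 24% | 12% |
| 0.9 | 13% | 7% |

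The favourable-direction column takes all biomarkers to be correlated in the direction of benefit. If the better of amount and concentration could be picked for each biomarker, the any-direction figures become 56%, 49%, 40% and 30% at correlations 0, 0.3, 0.5 and 0.7. That assumes a log-volume SD half the biomarker SD.

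**The case against.** The strongest reply is that this is a secondary outcome outside the stated hypotheses (Sections 2.1 and 5.1), that no 0.05 rule is set for it, and that a competent analyst would add a time term, an interaction and a sensible scale. Section 2.3's before-and-after wording points to a change contrast. That shows the intent, but Section 11.2c does not carry it into the model.

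Several stronger readings are tempting and should not be drawn:

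- *The named error families are wrong for continuous assay values.* Binomial and Poisson are given only as examples of an appropriate structure, so a Gaussian or log-scale model is allowed. No family or transformation is named for PISF, and no more than that can be said.
- *The model fails because it lists week 6.* A mixed model runs with a visit missing. The sentence giving the PISF visits also omits the week-6 clinical measurements required elsewhere, so it may not be a full schedule. No week-6 PISF sample is the natural reading, but not a certain one.
- *The plan uses an inefficient change score.* It states no change-score analysis for PISF, so the usual comparison of ANCOVA with change scores is not evidence against it.
- *The direction of effect will flip with the scale.* Both arms receive debridement, and a shared fall in volume cancels. A flip needs a between-arm volume difference that no document supplies.

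**Conclusion.** The point holds as a gap in a secondary analysis. The firmest part is the contrast: taken literally on two visits, the model estimates about half of a true week-12 difference. This rests on no baseline difference in expectation and on treatment being the only fixed factor, as written. The scale is undefined, which needs no assumption. That the two scales disagree in sign is possible but not shown.

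A reader might infer that a false biomarker claim is likely, or that a false benefit is close to an even chance. Neither follows. On one scale the chance of any false difference runs from about 13% (correlation 0.9) to 46% (independence), and it counts both directions; in the favourable direction it is at most about 26%. It passes one half only if the scale is also chosen afterwards and correlation is low (53% at correlation 0.2). All these figures assume testing at 0.05 per biomarker, which the plan does not state, and no true effect.

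**What to change.** In Section 11.2c, before any biomarker data are examined:

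1. Compare arms at week 12 by ANCOVA on the log value, adjusted for the log baseline value. Report geometric mean ratios with 95% intervals.
2. Name one scale (amount per timed strip, or concentration) as main and the other as sensitivity analysis. State how the four strips are pooled and how values below detection enter the log.
3. Either control the false discovery rate at 5% across the 12 biomarkers (Benjamini-Hochberg), or label them exploratory with no efficacy claim.

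In the simulations, Benjamini-Hochberg held the chance of any false finding under no true effect at 2.9% to 4.9%. Strict familywise control would be costly here. By two-sample t-test at 32 per arm, Bonferroni (0.05/12 = 0.0042) raises the difference detectable with 80% power from 0.71 to 0.96 SD and cuts power at 0.8 SD from 88% to 59%. The exploratory label is therefore a reasonable choice, but it does not remove the need for items 1 and 2.

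Cost: wording only, since volume and baseline values are already collected. Expect fewer nominally significant biomarkers. Section 12.2 requires IRB approval of the amendment.
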